5.4.4 Crude incidence and related risk estimates

5.4.4.1 Crude incidence and 100*(1- α)% confidence interval

For n subjects, each at risk to experience a certain event with probability π , the crude incidence is estimated as $p=x/n$, where x is the number of subjects with the event.

Absolute and relative frequencies will be displayed as well as 95% confidence interval for the relative frequency based on the score method including continuity correction ([Newcombe 1998](#)).

With Z as $(1-\alpha/2)$ -quantile of the standard normal distribution (SAS: $z=\text{PROBIT}(1-\alpha/2)$), n as total number of subjects (i.e. number of subjects in the denominator), and p as estimated crude incidence (number of subjects with event / n) it is $q=1-p$.

Then the lower limit is

$$L = \max \left(0, \frac{2np + z^2 - 1 - z\sqrt{z^2 - 2 - \frac{1}{n} + 4p(nq+1)}}{2(n+z^2)} \right)$$

and the upper limit is

$$U = \min \left(1, \frac{2np + z^2 + 1 + z\sqrt{z^2 + 2 - \frac{1}{n} + 4p(nq-1)}}{2(n+z^2)} \right).$$

Note: if $p = 0$ then $L = 0$ and if $p = 1$ then $U = 1$.

If appropriate, an exact $100*(1-\alpha)\%$ confidence interval ([Clopper-Pearson 1934](#)) will be obtained by using the SAS procedure PROC FREQ with the EXACT BINOMIAL statement. However, the confidence interval derived via the score method including continuity correction will be the default in safety analyses.

5.4.5 Exposure adjusted incidence rate and related risk estimates

5.4.5.1 Exposure adjusted incidence rate and $100*(1-\alpha)\%$ confidence interval

It will be assumed that for each of n subjects in a clinical trial the time t_j ($j=1, \dots, n$) to the first occurrence of a certain treatment emergent event is observed, or if the event was not experienced, the (censored) time to the end of the observation period or last dose plus 84 days whichever occur earlier. The sequence of first occurrences of an event will be modeled to follow approximately a Poisson process with constant intensity θ . The rate parameter θ will be

estimated as $\lambda=D/T$, where $T = \sum_{j=1}^n t_j$ and D is the number of subjects with at least one event.

Conditionally on T , an exact $100*(1-\alpha)\%$ confidence interval for a Poisson variable with parameter θT and observed value D can be obtained based on (Garwood, 1936), from which an exact $100*(1-\alpha)\%$ confidence interval for D/T will be derived as follows (Sahai, 1993; Ulm, 1990):

Lower confidence limit $L = \frac{0.5c_{\alpha/2,2D}}{T}$ for $D>0$, 0 otherwise,

Upper confidence limit $U = \frac{0.5c_{1-\alpha/2,2D+2}}{T}$

where $c_{\alpha,k}$ is the α th quantile of the Chi-square distribution with k degrees of freedom.

5.4.6 Primary analysis

Example schematic code for Bayesian analysis of 2311 using dummy data for PASI 75.

```
## model to fit placebo data

tau.prior <- rbind(c(0, 0.5), c(0, 1))

set.seed(345652)
analysis_pbo_mc_pasi <- gMAP(cbind(r, n-r) ~ 1 | trial,
                               tau.strata=stratum,
                               family=binomial,
                               data=final_data_pbo,
                               tau.dist="HalfNormal",
                               tau.prior=tau.prior,
                               beta.prior=rbind(c(0,2)))

## model to fit the data of A2311
set.seed(34535214)
analysis_A2311_mc_pasi75 <- gMAP(cbind(r, n-r) ~ 0 + TREATMENT,
                                    family=binomial,
                                    data=active,
                                    tau.dist="Fixed",
                                    tau.prior=1E-6,
                                    beta.prior=matrix(c(0,0,2,2), 2, 2))
```

5.4.7 Key secondary analysis

As per section 5.4.6 but on the PASI 90 endpoint.

5.4.8 Analysis of time-to-event data

Number and percentage of subjects with a clinical event based on the number of subjects in the analysis set at risk as denominator, will be provided by treatment group.

Subjects without PASI 75/90 response will be considered as censored at Week 12.

Median time to event and quartiles including 95% confidence intervals will be provided. The confidence intervals will be based on log-log transformation (PROC LIFETEST option conftype=log-log). The plot will include the number of subjects at risk for each treatment group at pre-specified timepoints, which are 0 to <= 4 weeks, >4 to <=8 weeks and 8 to <=12 weeks.

Subjects at risk, timepoint “0” and censoring will be defined as described in Table 5-1 below:

Table 5-1

Variable:	Risk set	Time = 0	Time of event	Censoring	Psoriasis ConMed*	Informative censoring
Time to						
PASI 75/90 response	All subjects randomized with baseline and post-baseline data for PASI	Date of randomization	Date of 1 st visit with PASI 75/90 response observed	Week 12 date/discontinuation date	Censor (if ConMed taken before the event)	No

Time-to-event will be derived as:

- date of event minus date of time=0 plus 1 day for subjects experiencing the event or
- date of censoring minus date of time=0 plus 1 day for subjects not experiencing the event

5.5 Rule of exclusion criteria of analysis sets

[figure not shown]
Protocol deviations for exclusion from analysis sets are defined in Table 5-2

[figure not shown]
Table 5-2 Subject classification rules

Analysis set	PD Categories Codes that cause subject to be excluded	Non-PD criteria that cause a subject to be excluded
Randomization set	NA	Misrandomized subject
FAS (Full Analysis Set)	DVSPID: INCL01; OTH12	Misrandomized subject
Safety	DVSPID: INCL01; OTH12	Misrandomized subject Subjects who did not take any study treatment

INCL01: ICF missing or not signed; in the case where ICF was obtained after initiating study procedures, subjects will be included in all analysis sets

OTH12: Severe ICH-GCP non-compliance of study site

6 Reference

Clopper CJ, Pearson ES (1934). The use of confidence or fiducial limits illustrated in the case of the binomial. *Biometrika*, 26; 404–413

Committee for medicinal products for human use (CHMP), European Medicines Agency for the Evaluation of Medicines for Human Use. (2004)

Guideline on clinical investigation of medicinal products indicated for the treatment of psoriasis. CHMP/EWP/2454/02 corr document. London, UK

Fredriksson T, Pettersson U (1978); Severe psoriasis – oral therapy with a new retinoid. *Dermatologica*; 157:238–44.

Little, R.J.A and Rubin, D.B. (2002). Statistical Analysis with Missing Data. Wiley Series in Probability and Statistics, Chapter 10

Newcombe RG (1998) Two-sided confidence intervals for the single proportion: comparison of seven methods. *Statistics in Medicine*; 17: 857-872.

Paller AS et al (2008) Etanercept treatment for children and adolescents with plaque psoriasis. *N Engl J Med*; 358:241-51.

Rubin, D.B. (1987). *Multiple Imputation for Nonresponse in Surveys*. New York: Wiley.

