#### **9.1 Analysis sets**

The following analysis sets will be used in this trial:

**Randomized set:** The randomized set will be defined as all subjects who were randomized at baseline visit. Unless otherwise specified, subjects with missing informed consent form as well as misrandomized subjects will be excluded from the randomized set.

Misrandomized subjects are subjects who are screen-failures, but have been randomized by the investigator before eligibility was finally assessed, however have not been treated. If subjects were re-screened and successfully randomized, they will be included in the randomized set according to the treatment assigned in the last randomization.

**Full analysis set (FAS):** The FAS will be comprised of all subjects from the randomized set to whom study treatment has been assigned. Following the intent-to-treat principle, subjects will be analyzed according to the treatment assigned to at randomization. If the actual randomization stratum is different to the assigned stratum in IRT, the actual stratum will be used in analyses. The subjects with severe GCP violation will not be included in the FAS.

Of note, subjects excluded from the randomized set will be excluded from the FAS.

**Safety set:** The safety set will include all subjects who took at least one dose of study drug during the treatment period. Subjects will be analyzed according to treatment received.

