2.2 Analysis sets

The following analysis sets will be used for the data analysis.

Randomized set: The randomized set will be defined as all subjects who were randomized at baseline visit. Unless otherwise specified, misrandomized subjects will be excluded from the randomized set.

Misrandomized subjects are subjects who are screen-failures, but have been randomized by the investigator before eligibility was finally assessed, however have not been treated. If subjects were re-screened and successfully randomized, they will be included in the randomized set according to the treatment assigned in the last randomization.

Full analysis set (FAS): The FAS will be comprised of all subjects from the randomized set to whom study treatment has been assigned. Following the intent-to-treat principle, subjects will be analyzed according to the treatment assigned to at randomization. If the actual randomization stratum is different to the assigned stratum in Interactive Response Technology system (IRT), the actual stratum will be used in analyses. Subjects reporting a severe GCP (good clinical practice) violation will be excluded from the FAS.

Of note, subjects excluded from the randomized set will be excluded from the FAS.

Safety set: The safety set includes all subjects who took at least one dose of study treatment during the treatment period. For safety summaries, subjects will be analyzed according to treatment received. The treatment received will be set to the treatment randomized. But if a subject has received the wrong treatment during the entire study, the treatment received will be set to this wrong treatment. If a subject has received intermittent wrong treatment, the treatment received will be set to the original randomized treatment.

For those subjects who received erroneously the wrong treatment at least once, an additional listing will be prepared flagging adverse events which occurred after the treatment deviation.

Protocol deviations leading to exclusion from analysis populations are defined in Table 5-2 in Section 5 Appendix.

The number of subjects in each analysis set will be presented for all treatment groups in efficacy and safety analyses, and for all subjects (total). The number of screened and screen failures subjects will also be shown for all subjects (total).

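### Table 5-2 of the SAP excludes dosed subjects at severely non-compliant sites from the Safety set, contrary to Protocol 9.1 and SAP 2.2, and SAP section 4 does not list the departure

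*SAP*

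**What the plan says.** Protocol 9.1 defines the Safety set by exposure alone: "The safety set will include all subjects who took at least one dose of study drug during the treatment period". In the same section the GCP exclusion is tied to a different set: "The subjects with severe GCP violation will not be included in the FAS".

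SAP 2.2 repeats both parts. The Safety set is again defined by dosing ("The safety set includes all subjects who took at least one dose of study treatment during the treatment period"), and the GCP rule again names only the FAS: "Subjects reporting a severe GCP (good clinical practice) violation will be excluded from the FAS". SAP 2.2 then hands the detail to the appendix: "Protocol deviations leading to exclusion from analysis populations are defined in Table 5-2 in Section 5 Appendix".

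In Table 5-2 (SAP 5.5) the FAS row and the Safety row carry identical deviation codes, "DVSPID: INCL01; OTH12". The footnotes define INCL01 as a missing or unsigned consent form, and the other code as "OTH12: Severe ICH-GCP non-compliance of study site". The Safety row also lists, in a separate column, misrandomized subjects and subjects who took no study treatment. The table is the same in the July 2020 and September 2023 SAPs.

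SAP 2.8 bases all safety analyses on the Safety set, and SAP 2.4.1 does the same for exposure.

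**The concern.** The definition and the table that implements it give different Safety sets. A programmer who follows Table 5-2 will drop children who consented and were dosed, because of how their site behaved. Nothing in the protocol provides for that.

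Long-term safety in children is a stated purpose of this trial, which is small and open-label. An excluded subject leaves both numerator and denominator of every safety table, including deaths and the AE/SAE tables for registry posting. The documents supplied give no criterion for when non-compliance is severe and no deadline for assigning the code. Protocol 5.4 says blinding does not apply to any party. A judgement made under those conditions should not decide whose adverse events are counted.

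**Working it through.** The plan states no figure for this point, so the check is a comparison of texts followed by simple arithmetic for scale.

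**Comparison of the rules**

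| Source | Who is in the Safety set | Where the GCP exclusion applies |
|---|---|---|
| Protocol 9.1 | everyone dosed at least once | FAS only, worded by subject |
| SAP 2.2 | everyone dosed at least once | FAS only, worded by subject |
| SAP Table 5-2 | dosed subjects without INCL01 or OTH12 | FAS and Safety set, coded by site |

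1. Taking no study treatment is a separate criterion in the Safety row, so OTH12 acts on subjects who were dosed.
2. SAP 2.2 refers to Table 5-2 for exclusions, so the table would be followed in programming.
3. SAP section 4 lists changes to protocol-specified analyses: the imputation method, the scope of the Week 16 analysis, the added Week 24 analysis and subgroup summaries, and COVID-19 reporting. It does not mention the Safety set.
4. The table of protocol deviations (SAP 2.3.1) is run on the FAS, which also excludes OTH12. That table would therefore not show these subjects.
5. The FAS row has a smaller mismatch of its own. Protocol 9.1 and SAP 2.2 exclude subjects with a severe GCP violation, whereas OTH12 is defined at site level.

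**Scale**

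Inputs: about 80 subjects and about 40 centres (Protocol 3.1, SAP 1.1), and a target of at least 5 subjects under 25 kg (same sections).

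- Subjects per average site: 80 / 40 = 2.
- Share of planned subjects lost per average site coded OTH12: 2 / 80 = 2.5%.
- The number of coded sites is not given. Assuming 1 to 8 average sites, the loss is 2 to 16 subjects, or 2.5% to 20%.
- One subject with an event is 1 / 80 = 1.25% of the planned set.
- Under 25 kg, for illustration only: 1 / 5 = 20% and 2 / 5 = 40%, if one or two of exactly five such children were at the excluded site.

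Chance of seeing at least one subject with an event of assumed true incidence 1%, as 1 − 0.99^n:

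- n = 80: 0.5525
- n = 78 (one site lost): 0.5434
- n = 72 (four sites lost): 0.5150
- n = 64 (eight sites lost): 0.4744

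One-sided 95% upper bound on incidence when no event is seen, as 1 − 0.05^(1/n): 0.0368 for n = 80 and 0.0377 for n = 78.

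Losing one site barely changes the average ability to detect an event. What matters is that a particular death or serious event at an excluded site would be missing from the tables.

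**The case against.** The strongest reply is that OTH12 marks sites whose data cannot be trusted. A site that under-records adverse events adds exposure without events and pulls crude and exposure-adjusted rates down. Removing it from numerator and denominator does not bias incidence unless its true risk differs. This stands as a reason to show results both ways. It does not justify the exclusion as the main rule, because the protocol applies the GCP exclusion to the FAS and not to the Safety set.

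The rule is also pre-specified. SAP 2.2 points to Table 5-2, which is unchanged between the two SAPs. A reader might infer a late or data-driven exclusion, and the documents do not support that. What remains is a contradiction that section 4 does not declare.

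A reader might also infer that the events would disappear altogether. That goes too far:

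- SAP 2.8.1 says all AEs are listed, although 2.8 bases safety analyses on the Safety set, so full coverage is arguable.
- Disposition uses the randomized set, for which Table 5-2 names no deviation-based exclusion.
- SAP 2.2 requires the size of each analysis set to be reported.
- Under Protocol 7.2.2, SAEs are reported to the sponsor whatever the analysis set.

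These keep the subjects partly visible, but they do not put the events back into the incidence tables.

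**Conclusion.** The contradiction is established on the text. As written, Table 5-2 narrows the Safety set below what Protocol 9.1 and SAP 2.2 define, and the change is undeclared.

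Its effect is conditional on a site with dosed subjects being coded OTH12. The documents do not say that this happened, so it cannot be claimed that any child's events were dropped. If it did happen, the size is about 2.5% of the planned 80 per average site, assuming subjects are spread evenly over 40 centres and all are dosed.

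It is tempting to say that one site could remove 20% to 40% of the lightest children. The documents do not support that as an estimate. Five is a minimum target, no site-by-weight distribution is given, and 40% requires both subjects at a two-subject site to weigh under 25 kg. It is a worst case only.

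INCL01 in the Safety row also departs from the dosing definition, but it rests on consent. Protocol 9.1 already removes subjects with missing consent from the randomized set.

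**What to change.** - Delete OTH12 from the Safety row of Table 5-2, so that it agrees with Protocol 9.1 and SAP 2.2.
- Flag subjects from OTH12 sites in the safety listings, and show the AE overview with and without them.
- Keep INCL01 in the Safety row, but state this exception in SAP 2.2.
- For the FAS, reconcile the subject-level wording of Protocol 9.1 and SAP 2.2 with the site-level code.

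If the sponsor prefers to keep OTH12 in the Safety row, SAP 2.2 and section 4 should state and justify it, and the AEs, SAEs and deaths of the excluded dosed subjects should be reported separately.

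The preferred change costs one table entry, one sentence in SAP 2.2 on consent, a listing flag and one repeated overview table. Its small downside is that data from a poor-quality site, which may under-record AEs, enter the main safety tables. The paired overview shows how much that matters.
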